APPENDIX D LABORATORY NORMAL REFERENCE RANGES

HEMATOLOGY

Laboratory Parameter (Unit)	Normal Reference Range
Absolute basophils, cells/uL	Male gender, Age to 133Y: 0-200 Female gender, Age to 133Y: 0-200
Absolute eosinophils, cells/uL	Male gender, Age to 133Y: 15-500 Female gender, Age to 133Y: 15-500
Absolute lymphocytes, cells/uL	Male gender, Age to 18Y: 1200-5200 Male gender, Age to 133Y: 850-3900 Female gender, Age to 18Y: 1200-5200 Female gender, Age to 133Y: 850-3900
Absolute monocytes, cells/uL	Male gender, Age to 18Y: 200-900 Male gender, Age to 133Y: 200-950 Female gender, Age to 18Y: 200-900 Female gender, Age to 133Y: 200-950
Absolute neutrophils, cells/uL	Male gender, Age to 18Y: 1800-8000 Male gender, Age to 133Y: 1500-7800 Female gender, Age to 18Y: 1800-8000 Female gender, Age to 133Y: 1500-7800
Erythrocytes, (million/uL)	Male gender, Age to 18Y: 4.10-5.70 Male gender, Age to 133Y: 4.20-5.80 Female gender, Age to 18Y: 3.80-5.10 Female gender, Age to 133Y: 3.80-5.10
Hematocrit, %	Male gender, Age to 18Y: 36.0-49.0 Male gender, Age to 133Y: 38.5-50.0 Female gender, Age to 18Y: 34.0-46.0 Female gender, Age to 133Y: 35.0-45.0

Laboratory Parameter (Unit)	Normal Reference Range
Hemoglobin, g/dL	Male gender, Age to 18Y: 12.0-16.9 Male gender, Age to 133Y: 13.2-17.1 Female gender, Age to 18Y: 11.5-15.3 Female gender, Age to 133Y: 11.7-15.5
Mean Corpuscular Hemoglobin (pg)	Male gender, Age to 18Y: 25.0-35.0 Male gender, Age to 133Y: 27.0-33.0 Female gender, Age to 18Y: 25.0-35.0 Female gender, Age to 133Y: 27.0-33.0
Mean Corpuscular Volume (fL)	Male gender, Age to 18Y: 78.0-98.0 Male gender, Age to 133Y: 80.0-100.0 Female gender, Age to 18Y: 78.0-98.0 Female gender, Age to 133Y: 80.0-100.0
Leukocytes, (thousands/uL)	Male gender, Age to 18Y: 4.10-5.70 Male gender, Age to 133Y: 4.20-5.80 Female gender, Age to 18Y: 3.80-5.10 Female gender, Age to 133Y: 3.80-5.10
Platelet count, thousands/uL	Male gender, Age to 133Y: 140-400 Female gender, Age to 133Y: 140-400

SERUM CHEMISTRY

Laboratory Parameter ,Unit	Normal Reference Range
Alanine aminotransferase, U/L	Male gender, Age to 133Y: 9-46 Female gender, Age to 133Y: 6-29
Albumin, g/dL	Male gender, Age to 133Y: 3.6-5.1 Female gender, Age to 133Y: 3.6-5.1
Alkaline phosphatase, U/L	Male gender, Age to 19Y: 46-169 Male gender, Age to 49Y: 36-130 Male gender, Age to 133Y: 35-144

Laboratory Parameter ,Unit	Normal Reference Range
	Female gender, Age to 19Y: 36-128 Female gender, Age to 49Y: 31-125 Female gender, Age to 133Y: 37-153
Aspartate Aminotransferase, U/L	Male gender, Age to 133Y: 7-25 Female gender, Age to 133Y: 7-25
Amylase, U/L	Male gender, Age to 133Y: 21-101 Female gender, Age to 133Y: 21-101
Bilirubin total, mg/dL	Male gender, Age to 133Y: NEGATIVE Female gender, Age to 133Y: NEGATIVE
Blood urea nitrogen, mg/dL	Male gender, Age to 19Y: 7-20 Male gender, Age to 133Y: 7-25 Female gender, Age to 19Y: 7-20 Female gender, Age to 133Y: 7-25
Calcium, mg/dL	Male gender, Age to 19Y: 8.9-10.4 Male gender, Age to 133Y: 8.6-10.3 Female gender, Age to 19Y: 8.9-10.4 Female gender, Age to 49Y: 8.6-10.2 Female gender, Age to 133Y: 8.6-10.4
Carbon dioxide , mmol/L	Male gender, Age to 133Y: 20-32 Female gender, Age to 133Y: 20-32
Chloride, mmol/L	Male gender, Age to 133Y: 98-110 Female gender, Age to 133Y: 98-110

Laboratory Parameter ,Unit	Normal Reference Range
Creatinine, mg/dL	Male gender, Age to 19Y: 0.60-1.26 Male gender, Age to 49Y: 0.60-1.35 Male gender, Age to 59Y: 0.70-1.33 Male gender, Age to 69Y: 0.70-1.25 Male gender, Age to 79Y: 0.70-1.18 Male gender, Age to 133Y: 0.70-1.11 Female gender, Age to 19Y: 0.50-1.00 Female gender, Age to 49Y: 0.50-1.10 Female gender, Age to 59Y: 0.50-1.05 Female gender, Age to 69Y: 0.50-0.99 Female gender, Age to 79Y: 0.60-0.93 Female gender, Age to 133Y: 0.60-0.88
Creatinine Clearance, Estimated, mL/min	Male gender, Age to 133Y: >/=90 mL/Min Female gender, Age to 133Y: >/=90 mL/Min
Glucose, nonfasting, mg/dL	Male gender, Age to 133Y: 65-139 Female gender, Age to 133Y: 65-139
Lactate dehydrogenase, U/L	Male gender, Age to 49Y: 100-220 Male gender, Age to 133Y: 120-250 Female gender, Age to 49Y: 100-200 Female gender, Age to 133Y: 120-250
Lipase, U/L	Male gender, to 133Y: 7-60 Female gender, to 133Y: 7-60
Phosphorus, mg/dL	Male gender, Age 18Y: 3.0-5.1 Male gender, Age 20Y: 2.7-5.0 Male gender, Age to 64Y: 2.5-4.5 Male gender, Age to 133Y: 2.1-4.3 Female gender, Age: 18Y: 3.0-5.1 Female gender, Age: 20Y: 2.7-5.0 Female gender, Age to 64Y: 2.5-4.5 Female gender, Age to 133Y: 2.1-4.3

Laboratory Parameter ,Unit	Normal Reference Range
Potassium, mmol/L	Male gender, Age to 19Y: 3.8-5.1 Male gender, Age to 133Y: 3.5-5.3 Female gender, Age to 19Y: 3.8-5.1 Female gender, Age to 133Y: 3.5-5.3
Protein total, g/dL	Male gender, Age to 19Y: 6.3-8.2 Male gender, Age to 133Y: 6.1-8.1 Female gender, Age to 19Y: 6.3-8.2 Female gender, Age to 133Y: 6.1-8.1
Sodium, mmol/L	Male gender, Age to 133Y: 135-146 Female gender, Age to 133Y: 135-146
Serum beta human chorionic gonadotropin (β-hCG), TOTAL, QL	Male gender, Age to 133Y: NEGATIVE Female gender, Age to 133Y: Non-Pregnant: Negative; Pregnant: Positive
Follicle-stimulating hormone (FSH)	Female gender, Age to 133Y: Follicular Phase: 2.5-10.2 Mid-cycle Phase: 3.1-17.7 Luteal Phase: 1.5-9.1 Postmenopausal: 23.0-116.3

LIPIDS

Laboratory Parameter , Unit	Normal Reference Range
Triglycerides, mg/dl	Male gender, Age to 19Y: <90 Male gender, Age to 133Y: <150 Female gender, Age to 19Y: <90 Female gender, Age to 133Y: <150
Low Density Lipoprotein (LDL), mg/dl	Male gender, Age to 19Y: <110 Male gender, Age to 133Y: <100 Female gender, Age to 19Y: <110 Female gender, Age to 133Y: <100

Cholesterol, Total, mg/dl	Male gender, Age to 19Y: >45 Male gender, Age to 133Y: > OR = 40 Female gender, Age to 19Y: >45 Female gender, Age to 133Y: > OR = 50
---------------------------	--

COAGULATION

Laboratory Parameter , Unit	Normal Reference Range
Activated partial thromboplastin time, seconds	Male gender, Age to 133Y: 23-32 Female gender, Age to 133Y: 23-32
Prothrombin, International normalized ratio (INR), Ratio	Male gender, Age to 133Y: 0.9-1.1 Female gender, Age to 133Y: 0.9-1.1
Prothrombin Time, seconds	Male gender, Age to 133Y: 9.0-11.5 Female gender, Age to 133Y: 9.0-11.5

COMPLEMENT ACTIVATION

Laboratory Parameter , Unit	Normal Reference Range
Complement Component C3C (C3, C4, CH50), mg/dl	Male gender, Age to 80Y: 82-193 Male gender, Age > or = 81Y: Not Established Female gender, Age to 80Y: 82-193 Female gender, Age > or = 81Y: Not Established

URINALYSIS

Laboratory Parameter	Normal Reference Range
Appearance	Male gender, Age to 133Y: CLEAR Female gender, Age to 133Y: CLEAR
Bilirubin	Male gender, Age to 133Y: Negative Female gender, Age to 133Y: Negative
Color	Male gender, Age to 133Y: YELLOW Female gender, Age to 133Y: YELLOW
Erythrocyte (/HPF)	Male gender, Age to 133Y: < or = 2 Female gender, Age to 133Y: < or = 2
Glucose	Male gender, Age to 133Y: Negative Female gender, Age to 133Y: Negative
Ketones	Male gender, Age to 133Y: Negative Female gender, Age to 133Y: Negative
Leukocyte Esterase	Male gender, Age to 133Y: Negative Female gender, Age to 133Y: Negative
Nitrite	Male gender, Age to 133Y: Negative Female gender, Age to 133Y: Negative
Occult Blood	Male gender, Age to 133Y: Negative Female gender, Age to 133Y: Negative
pH	Male gender, Age to 133Y: 5.0-8.0 Female gender, Age to 133Y: 5.0-8.0
Protein	Male gender, Age to 133Y: Negative Female gender, Age to 133Y: Negative
Specific Gravity	Male gender, Age to 133Y: 1.001-1.035 Female gender, Age to 133Y: 1.001-1.035

SEROLOGY

Laboratory Parameter , Unit	Normal Reference Range
Hepatitis B surface antigen (HBsAg)	Male gender, Age to 133Y: NON-REACTIVE Female gender, Age to 133Y: NON-REACTIVE
Hepatitis C antibody	Male gender, Age to 133Y: NON-REACTIVE Female gender, Age to 133Y: NON-REACTIVE
Human immunodeficiency virus (HIV) antibody	Male gender, Age to 133Y: NON-REACTIVE Female gender, Age to 133Y: NON-REACTIVE

OTHER

Laboratory Parameter , Unit	Normal Reference Range
Opioids	Male gender, Age to 133Y: NEGATIVE Female gender, Age to 133Y: NEGATIVE
Benzodiazepines	Male gender, Age to 133Y: NEGATIVE Female gender, Age to 133Y: NEGATIVE
Barbiturates	Male gender, Age to 133Y: NEGATIVE Female gender, Age to 133Y: NEGATIVE
Cocaine metabolites	Male gender, Age to 133Y: NEGATIVE Female gender, Age to 133Y: NEGATIVE
Cannabinoids	Male gender, Age to 133Y: NEGATIVE Female gender, Age to 133Y: NEGATIVE
Methamphetamines	Male gender, Age to 133Y: NEGATIVE Female gender, Age to 133Y: NEGATIVE
Phencyclidine	Male gender, Age to 133Y: NEGATIVE Female gender, Age to 133Y: NEGATIVE

Amphetamine	Male gender, Age to 133Y: NEGATIVE Female gender, Age to 133Y: NEGATIVE
Cotinine, MCG/m:	Male gender, Age to 133Y: NEGATIVE Female gender, Age to 133Y: NEGATIVE
Alcohol	Male gender, Age to 133Y: NEGATIVE Female gender, Age to 133Y: NEGATIVE

TABLE, FIGURE, AND LISTING SHELLS

Cidara Therapeutics, Inc.

PROTOCOL No.: CD388.IM.SQ.1.01

A Phase 1, Randomized, Double-Blind, Single-Dose and Repeat Single Dose, Dose-Escalation Study to Determine the Safety, Tolerability, and Pharmacokinetics of CD388 Intramuscular or Subcutaneous Administration in Healthy Subjects

Protocol Version (Date): Amendment 2.0 (07-Feb-2023)

Altasciences Project No. CID-P1-144

Prepared by:

Altasciences Inc.
[name]
Laval, Quebec
Canada, H7V 4B3

Version: Final Amendment 3.0
Date: 2023-12-20

Version Control

Version	Date	Author	Description of Changes
1.0	2022-06-08	[name]/ [name]	Not applicable
1.1	2023-04-05	[name]/ [name]	A SAP is being updated due to the protocol amendment 2.0 (07-Feb-2023) which added a new cohort 4B for SQ route. All impacted sections are updated.

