Values for continuous laboratory parameters (hematology, chemistry, urinalysis, and coagulation) will be summarized by visit and for the change from baseline using descriptive statistics. The number and percentage of subjects with at least one post baseline PCS value and value that is PCS, for each scheduled post baseline of each laboratory parameter will also be presented. Serology, alcohol/drug screen, and pregnancy test results will be presented in separate listings.

Data listings will include out-of-range flags (L, H) and whether the abnormal values are clinically significant or not and an indication of whether the value meets the PCS criterion.

PCS values for laboratory parameters (as defined in [Table 8](#), [Table 9](#), [Table 10](#), [Table 11](#), [Table 12](#) below) will be listed by category. Normal reference ranges are presented in [APPENDIX D](#).

Table 8: PCS Values for Hematology

Laboratory Parameter (Unit)	PCS Range
Absolute basophils, cells/uL	> 400
Absolute eosinophils, cells/uL	> 800
Absolute lymphocytes, cells/uL	< 600
Absolute monocytes, cells/uL	< 10, > 2100
Absolute neutrophils, cells/uL	< or = 799, > 9000
Erythrocytes, (million/uL)	Male: < 3.8, > 6.4 Female: < 3.3, > 5.5

Laboratory Parameter (Unit)	PCS Range
Hematocrit, %	<20.0,>60.0
Hemoglobin, g/dL	Male: < 10 Female: < 9.5
Leukocytes, (thousands/uL)	< 2.0. > 25.0
Platelet count, thousands/uL	< 100,> 700

Table 9: PCS Values for Serum Chemistry

Laboratory Parameter ,Unit	PCS Range
Alanine aminotransferase, U/L	>or= 1.25 x ULN
Albumin, g/dL	<3.0,>6.0
Alkaline phosphatase, U/L	>or= 2.5 x ULN
Asparate Aminotransferase, U/L	>or= 1.25 x ULN
Amylase, U/L	>or= 1.5 x ULN
Bilirubin total, mg/dL	>or= 1.1 x ULN
Blood urea nitrogen, mg/dL	> 70
Calcium, mg/dL	<7.8,>or= 12.4
Carbon dioxide, mmol/L	<16,>40
Chloride, mmol/L	<65,> 130
Creatinine, mg/dL	> or = 1.1 x ULN
Creatinine Clearance, Estimated, mL/min	< 90
Glucose, nonfasting, mg/dL	<54,>160
Lipase, U/L	> or= 1.5 x ULN
Phosphorus, mg/dL	<2
Potassium, mmol/L	<3,>or=6
Protein total, g/dL	<3.0,>9.0
Sodium, mmol/L	<130,>or=150

Table 10 PCS Values for Lipids

Laboratory Parameter , Unit	PCS Range
Triglycerides, mg/dl	> 500
Low Density Lipoprotein (LDL), mg/dl	> or = 190
Cholesterol, Total, mg/dl	> = or 300

Table 11 PCS Values for Coagulation

Laboratory Parameter , Unit	PCS Range
Activated partial thromboplastin time, seconds	> or = 1.66 x ULN
Prothrombin, International normalized ratio (INR), Ratio	> or = 1.5 x ULN

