			x/xx (xx..x)		x/xx (xx..x)		x/xx (xx..x)		x/xx (xx..x)		x/xx (xx..x)		x/xx (xx..x)		x/xx (xx..x)		x/xx (xx..x)		x/xx (xx..x)		x/xx (xx..x)		x/xx (xx..x)			
			x/xx (xx..x)		x/xx (xx..x)		x/xx (xx..x)		x/xx (xx..x)		x/xx (xx..x)		x/xx (xx..x)		x/xx (xx..x)		x/xx (xx..x)		x/xx (xx..x)		x/xx (xx..x)		x/xx (xx..x)			
	Alanine aminotransfer ase (F)		x/xx (xx..x)		x/xx (xx..x)		x/xx (xx..x)		x/xx (xx..x)		x/xx (xx..x)		x/xx (xx..x)		x/xx (xx..x)		x/xx (xx..x)		x/xx (xx..x)		x/xx (xx..x)		x/xx (xx..x)			
	Alanine aminotransfer ase (M)		x/xx (xx..x)		x/xx (xx..x)		x/xx (xx..x)		x/xx (xx..x)		x/xx (xx..x)		x/xx (xx..x)		x/xx (xx..x)		x/xx (xx..x)		x/xx (xx..x)		x/xx (xx..x)		x/xx (xx..x)			

Date: VERSION - YYYY-MM-DD

Data Source: xxx

Program Source: xxx.sas

IM = Intramuscular; SQ = Subcutaneous

Note: n is the number of subjects who met the PCS criteria. Denominator (m) is the number of subjects with non-PCS baseline and at least one post-baseline assessment when calculating the percentage.

<Laboratory Panel> = Hematology; Chemistry; Urinalysis; Coagulation; Lipid;
<Programming Note>

ETC.= for SQ: Cohort 4B CD388 - Pooled Placebo
It can be presented separately (i.e., IM one page and SQ another).

Table 14.2.21 Teplate T5.1: Summary of Vital Signs (Safety Population)

Table 14.3.3.1
Summary of Vital Signs
(Safety Population)
<Parameter (Unit)>

Date: VERSION - YYYY-MM-DD Data Source: xxxx

Program Source: xxx.sas

IM = Intramuscular; SO = Subcutaneous; SD = Standard Deviation.

Note: Baseline is the measurement of the last predose measurement was used.

<Parameter (unit)> = Systolic Blood Pressure (mmHg), Diastolic Blood Pressure (mmHg), Pulse Rate (beats/min), Temperature (C), Respiratory Rate (breaths/min)

<Programming Note>

ETC.= for SO: Cohort 4B CD388 - Pooled Placebo

It can be presented separately (i.e., IM one page and SQ another).

Table 14.2.22 Template T5.2: Summary of Potentially Clinically Significant (PCS) Values Vital Signs (Safety Population)

Table 14.3.3.2
Number (Percentage) of Subjects with Potentially Clinically Significant (PCS) Values in Vital Signs at Post-baseline Visit
Safety Population

Parameter / PCS TimepointCriteria	IM Route				SQ Route				ETC. (N = XX)
	CD388 50 mg (N = XX)	CD388 150 mg (N = XX)	CD388 450 mg (N = XX)	Pooled Placebo (N = XX)	CD388 50 mg (N = XX)	CD388 150 mg (N = XX)	CD388 450 mg (N = XX)	CD388 900 mg (N = XX)	
	n/m (%)	n/m (%)	n/m (%)	n/m (%)	n/m (%)	n/m (%)	n/m (%)	n/m (%)	

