Subjects with at least one PCS Value									
Systolic Blood Pressure									
<=90 mmHg	x (xx.x)	x (xx.x)	x (xx.x)	x (xx.x)	x (xx.x)	x (xx.x)	x (xx.x)	x (xx.x)	x (xx.x)
>=140 mmHg	x (xx.x)	x (xx.x)	x (xx.x)	x (xx.x)	x (xx.x)	xxxx.x	x (xx.x)	x (xx.x)	xxxx.x
Diastolic Blood Pressure									
<=60 mmHg	x (xx.x)	x (xx.x)	x (xx.x)	x (xx.x)	x (xx.x)	x (xx.x)	x (xx.x)	x (xx.x)	x (xx.x)
>=90 mmHg	x (xx.x)	x (xx.x)	x (xx.x)	x (xx.x)	x (xx.x)	x (xx.x)	x (xx.x)	x (xx.x)	x (xx.x)
Pulse Rate									
<=50 beats/min	x (xx.x)	x (xx.x)	x (xx.x)	x (xx.x)	x (xx.x)	x (xx.x)	x (xx.x)	x (xx.x)	x (xx.x)
>=100 beats/min	x (xx.x)	x (xx.x)	x (xx.x)	x (xx.x)	x (xx.x)	x (xx.x)	x (xx.x)	x (xx.x)	x (xx.x)
...									
Pre-Dose Systolic Blood Pressure									
<=90 mmHg	x (xx.x)	x (xx.x)	x (xx.x)	x (xx.x)	x (xx.x)	x (xx.x)	x (xx.x)	x (xx.x)	x (xx.x)
>=140 mmHg	x (xx.x)	x (xx.x)	x (xx.x)	x (xx.x)	x (xx.x)	x (xx.x)	x (xx.x)	x (xx.x)	x (xx.x)
Diastolic Blood									

Pressure

<=60 mmHg	x (xx.x)								
>=90 mmHg	x (xx.x)								

Pulse Rate

<=50 beats/min	x (xx.x)								
>=100 beats/min	x (xx.x)								

...

Date: VERSION - YYYY-MM-DD

Data Source: xxxx

Program Source: xxxx.sas

IM = Intramuscular; SQ = Subcutaneous.

Note: n is the number of subjects who met the PCS criteria. Denominator (m) is the number of subjects with non-PCS baseline and at least one post-baseline assessment when calculating the percentage.

<Programming Note>

ETC.= for SQ: Cohort 4B CD388 - Pooled Placebo

It can be presented separately (i.e., IM one page and SQ another).

Table 14.2.24 Template T5.3: ECG: Observed Values and Changes from Baseline (Safety Population)

Table 14.3.4.1
 ECG: Observed Values and Changes from Baseline
 (Safety Population)
 <Parameter (Unit)>

Visit	Timepoint	IM Route								SQ Route							
		CD388 50 mg (N = XX)		CD388 150 mg (N = XX)		CD388 450 mg (N = XX)		Pooled Placebo (N = XX)		CD388 50 mg (N = XX)		CD388 150 mg (N = XX)		CD388 450 mg (N = XX)		ETC. (N = XX)	
		Observ ed	Change from Baseli ne	Observ ed	Change from Baseli ne	Observ ed	Change from Baseli ne	Observ ed	Change from Baseli ne	Observ ed	Change from Baseli ne	Observ ed	Change from Baseli ne	Observ ed	Change from Baseli ne	Observ ed	Change from Baseli ne
Baseline	n	xx	xx	xx	xx	xx	xx	xx	xx	xx	xx	xx	xx	xx	xx	xx	xx

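### SAP Appendix D gives leukocytes the red-cell range and serum bilirubin no numeric limit; separately, the PCS tables count in n subjects whom m excludes, so percentages can exceed 100%

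*SAP*

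**What the plan says.** **Normal ranges.** SAP Section 8.2 states: "Data listings will include out-of-range flags (L, H) and whether the abnormal values are clinically significant or not". It then refers to Appendix D for the normal reference ranges, and listing shell L9.1 has a High/Low column. The relevant Appendix D rows are:

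- The Leukocytes row, whose unit is thousands/uL, reads as follows: "Male gender, Age to 18Y: 4.10-5.70 Male gender, Age to 133Y: 4.20-5.80 Female gender, Age to 18Y: 3.80-5.10 Female gender, Age to 133Y: 3.80-5.10". The Erythrocytes row, in million/uL, has the same four bands and limits.
- Absolute neutrophils, cells/uL, adult men: "Male gender, Age to 133Y: 1500-7800". The adult female range is the same.
- Serum total bilirubin, mg/dL: "Male gender, Age to 133Y: NEGATIVE Female gender, Age to 133Y: NEGATIVE". SAP Table 9 makes this analyte PCS at 1.1 x ULN or more.
- Total cholesterol, mg/dL, men: "Male gender, Age to 19Y: >45 Male gender, Age to 133Y: > OR = 40". The female bands are also lower limits only.
- Complement: a single range under the label "Complement Component C3C (C3, C4, CH50), mg/dl".

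**PCS percentages.** The notes under shells T4.2 (laboratory) and T5.2 (vital signs) define the numerator as "n is the number of subjects who met the PCS criteria" and continue "Denominator (m) is the number of subjects with non-PCS baseline and at least one post-baseline assessment when calculating the percentage". Section 8.2 and Table 6 count subjects with at least one post-baseline PCS value and set no baseline condition. Both shells carry Pre-Dose rows. Section 10.3 takes the last non-missing value before the first dose as baseline.

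**The concern.** These are two separate defects.

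First, the leukocyte range cannot be a white-cell range, because one component of the count may be normal at a value above the limit for the total. If the flags are programmed from Appendix D, the white-cell listing fills with false High flags. For bilirubin, a multiple of NEGATIVE has no value, so the programmer must find the limit outside the SAP. The SAP's version history says version 3.0 was issued to bring the reference and PCS ranges into line with the study laboratory, so these rows miss that aim.

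Second, n and m refer to different sets of subjects. A subject who is PCS at baseline and stays so enters n but not m. The percentage then presents a pre-existing value as if it were new, and nothing keeps it at or below 100%.

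Laboratory tests and vital signs are part of the primary safety endpoint. With 8 CD388 subjects per column, one misplaced subject moves a percentage visibly.

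**Working it through.** **1. Leukocytes.** Adult differential ranges from Appendix D, cells/uL:

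| | Lower | Upper | Midpoint |
|---|---|---|---|
| Neutrophils | 1,500 | 7,800 | 4,650 |
| Lymphocytes | 850 | 3,900 | 2,375 |
| Monocytes | 200 | 950 | 575 |
| Eosinophils | 15 | 500 | 257.5 |
| Basophils | 0 | 200 | 100 |
| Sum | 2,565 | 13,350 | 7,957.5 |

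In thousands/uL the components span 2.57 to 13.35 with midpoint 7.96. The printed leukocyte ranges are 4.20–5.80 (men) and 3.80–5.10 (women).

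The printed limits do fit red cells. Dividing 10 x haematocrit by them gives 10 x 38.5/4.20 = 91.7 and 10 x 50.0/5.80 = 86.2 fL for men, and 10 x 35.0/3.80 = 92.1 and 10 x 45.0/5.10 = 88.2 fL for women. All lie inside the SAP's own MCV range of 80–100. So the Leukocytes row is the wrong one.

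The share flagged High depends on assumptions. With independent components and 2,000,000 simulated draws:

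| Differential ranges read as | P(WBC > 5.80), men | P(WBC > 5.10), women |
|---|---|---|
| Uniform limits | 0.83 | 0.91 |
| Normal 95% interval | 0.88 | 0.94 |
| Lognormal 95% interval (basophils normal) | 0.58 | 0.75 |

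The leukocyte PCS rule uses fixed cut-offs (below 2.0, above 25.0) and is unaffected.

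**2. Bilirubin.** The ULN-based PCS rules are ALT, ALP, AST, amylase, bilirubin, creatinine and lipase (Table 9), and aPTT, INR and PT (Table 11): 7 + 3 = 10. Nine have a numeric upper limit in Appendix D. Bilirubin does not.

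**3. Cholesterol and complement.** With lower limits only, total cholesterol can never be flagged High, although its PCS rule (300 or more) still works. Complement has one mg/dL range for three tests.

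**4. Baseline PCS values are realistic.**

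- Protocol Section 7.1 admits creatinine clearance of 80 mL/min or more, while Table 9 makes a value below 90 PCS.
- Eligibility sets no numeric vital-sign limits, while Table 13 makes diastolic pressure of 60 or less, and respiratory rate of 12 or less or 20 or more, PCS.

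**5. n/m as written.** Let k of 8 subjects be PCS at baseline and remain so, with no new cases. As written the result is k/(8 − k); with n taken within m it is 0/(8 − k).

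| k (assumed) | m | As written | n within m |
|---|---|---|---|
| 1 | 7 | 14.3% | 0% |
| 2 | 6 | 33.3% | 0% |
| 3 | 5 | 60.0% | 0% |
| 4 | 4 | 100.0% | 0% |
| 5 | 3 | 166.7% | 0% |

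Pooled placebo behaves the same way: 5/4 = 125% in the IM column of 9, and 7/5 = 140% in the SQ column of 12.

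**6. Pre-Dose row, first dose, T5.2.** When the predose value is the baseline, everyone counted in n is excluded from m. Three such subjects of 8 give 3/5 = 60%, against a true 3/8 = 37.5%.

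**The case against.** The strongest reply is that little of this reaches a summary table. Section 8.2 does not say that the flags are derived from Appendix D, and the laboratory may supply them. T4.1 and T4.2 do not use L/H flags, no shift table is planned, and L9.1 has its own clinical-significance column. The laboratory must hold a bilirubin ULN, since the protocol applies multiples of it at screening and for fractionation. Lipids and complement are scheduled only at screening and when clinically indicated; complement has no PCS rule and is not among the panels named for T4.1, T4.2 or L9.1.

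On n/m, a programmer may take n within m by convention, the shells allow footnotes to change, and the Pre-Dose rows may be template residue in tables titled as post-baseline. Screening limits also make baseline PCS uncommon for several chemistry tests. Exceeding 100% needs many baseline cases: in an arm of 8, with 80% persistence and 10% new cases (assumed), the probability is 0.001 at 10% baseline PCS and 0.038 at 25%, rising to 0.362 at 50%.

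Most of this stands as a limit on impact. It does not make the rows correct. The SAP states neither that the laboratory supplies the flags nor that n lies within m, and its body text also leaves n unrestricted. Percentages below 100% are the greater hazard because they look plausible: one persistent case prints 14.3% where no new case occurred.

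**Conclusion.** The point holds. The Leukocytes row is a copy of the Erythrocytes row and contradicts the appendix's own differential ranges. Serum bilirubin has no ULN in the SAP although its PCS rule needs one. The total cholesterol and complement rows are also wrong, with less consequence. The T4.2 and T5.2 notes do not make n a subset of m.

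The false High flags arise only if the flags follow Appendix D. The ranges of 58–88% of men and 75–94% of women rest on independent components and three assumed distributions; the contradiction with the neutrophil limit does not. The n/m examples use assumed counts, but the formula follows from the notes as written. No hypothesis test is affected and most PCS rules work as printed. The errors should be corrected because they touch the display of the primary safety endpoint and cost little to remove.

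**What to change.** 1. In Appendix D, replace the Leukocytes, serum total bilirubin, total cholesterol and complement rows with the study laboratory's actual ranges, giving C3, C4 and CH50 separate rows. The correct values are not in the protocol or SAP.
2. In the notes to T4.2 and T5.2, define n as the subjects among m who meet the PCS criterion after baseline, and bring the wording of Section 8.2 and Table 6 into line.
3. Remove the Pre-Dose rows from both tables, or give them their own denominator: all subjects with a predose value.

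The cost is four appendix rows, two shell notes with matching text, and a re-run of the flags and PCS tables. No new data are needed.
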